4.0 Abstract

Title: Real-World Outcome of Rheumatoid Arthritis Patients in Korea on adalimumab (ROCKA Study).

Rationale and Background: Given the requirement to keep a balance between effectiveness and cost containment to ensure that the available health resources are used in a cost-effective manner, there is an increasing demand for real-world evidence (RWE) from policy makers, regulators, providers and payers in the region to optimize spending and patient outcomes.

So far, there are no data available regarding adalimumab's impact on patients' quality of life (QoL) and healthcare resource utilization (HCRU) in a realistic study design in Korea.

The goal of this study is to determine the QoL, HCRU and costs of the patients care in subjects with RA who are treated with adalimumab in Korea.

Results from study on the effect of adalimumab on Work Productivity and Activity Impairment (WPAI) scores and other Patient-Reported Outcomes (PROs) will be of interest to a variety of stakeholders in the healthcare system including patients, healthcare practitioners and payers in Korea.

Research Question and Objectives: The objective of this non-interventional, observational study is to assess the effect of adalimumab on health-related QoL and work productivity in patients with Rheumatoid Arthritis (RA) in Korea. Specifically, to achieve the above objective the following concrete steps will be taken:

1. Recruit investigators who are willing and able to recruit and follow new adalimumab users for 6 months follow-up
2. Collect the patients' clinical profile, patient-reported QoL, functioning, work productivity, treatment satisfaction and HCRU of RA patients at adalimumab initiation
3. Follow the patients initiating adalimumab for 24 weeks and identify the changes in clinical, economic, and PROs associated with adalimumab

Study Design: The study is designed as a prospective, observational study to assess the effect of adalimumab on health-related QoL and work productivity in patients with RA in Korea.

Note: This study is non-interventional and the subjects/investigators will follow the current clinical practice in each site and also the routine clinical follow up as determine by the treating physician.

RA patients, for whom adalimumab treatment has already been decided, will be recruited from within the clinical settings of each rheumatologist participating in the study. Approximately 89 patients diagnosed with RA that meet the inclusion and exclusion criteria will be enrolled at approximately 9 sites in Korea.

To assess health and disability outcomes, the Health Assessment Questionnaire Disability Index (HAQ DI) will be assessed at baseline, Week 12 and Week 24 after treatment initiation with adalimumab. In addition, other PROs of work activity and well-being, including the WPAI, EuroQol 5 dimension (EQ-5D), and Short Form 36-Item Health Survey (SF-36), will also be assessed.

In addition, the health care resource utilization will be collected. This includes surgical procedures, hospitalizations, bed days in hospital, physician consultations etc. Costs will be assigned based on the health care resource utilization using standardized costs for participating country.

Population: Subjects will be males and/or females who are attending a routine clinical visit and meet all of the inclusion criteria and none of the exclusion criteria. Approximately 89 patients diagnosed with RA will be recruited.

Inclusion Criteria:

Patients meeting all of the following inclusion criteria at baseline will be included:

1. Subject has a diagnosis of RA as defined by the 1987 revised American College of Rheumatology (ACR) classification criteria and/or the ACR/the European League against Rheumatism (EULAR) 2010 classification criteria (any duration since diagnosis).
2. Male or female subject ≥ 18 years of age (local definition according to adalimumab label) who is in compliance with eligibility for adalimumab based on the local label.
3. Patients with moderate to severe RA defined as Disease Activity Score in 28 Joints (DAS28) (ESR) or DAS28 (CRP) > 3.2
4. Biologically treatment naïve and initiated adalimumab at baseline visit
5. Availability of clinical data of the previous 12 weeks prior to baseline
6. Ability to self-complete patient questionnaires
7. Subject must be able and willing to provide written informed consent and comply with the requirements of this study protocol.

Exclusion Criteria:

Patients meeting any of the following exclusion criteria at baseline will be excluded:

1. Patients who are pregnant or breast feeding at enrolment or wish to become pregnant in the next 24 weeks.


2. Participation in any RA-related clinical trial at the time of enrolment, at baseline or at any point during the past 24 weeks prior to baseline3. Patients, who in the clinician's view, may not be able to accurately report their QoL or prior resource utilization4. Patients, who in the clinician's view, may not be able to adhere to adalimumab therapy over 24 weeks.
--

Variables:**Primary Variable**

- Change in HAQ DI score at weeks 12 and weeks 24 weeks from the baseline

Secondary Variable

- Change in other PROs (SF-36 domain scales, EQ-5D Index, Work Productivity and Activity Impairment Questionnaire [WPAI]) from baseline to weeks 12 and 24
- Number and percent of patients achieving a clinically meaningful improvement on the HAQ DI, from baseline to weeks 12 and 24
- Healthcare Resource Utilization (HCRU) at baseline, 12 and 24 weeks

Additional Secondary Variable

- Change in HAQ DI score from baseline to 24 weeks
- Changes in the disease severity and PROs from baseline to 24 weeks

Exploratory Variable

- Change in patient satisfaction questions from baseline to weeks 12 and 24

Data Sources: Case Report Forms (CRFs) and patient questionnaires. Collection of data includes but not limited to subject demographics, clinical history, comorbidities, spontaneous adverse events, and concomitant medications. The following questionnaires will be utilized to collect data directly from participating subjects:

- EQ-5D
- SF-36
- HAQ DI
- WPAI
- HCRU
- Patient Global Impression of Change (PGIC)
- Patient Treatment Satisfaction Questions

Study Size: Approximately 89 patients diagnosed with RA that meet the inclusion and exclusion criteria will be enrolled at approximately 9 sites in Korea. The sample size was calculated by assuming an alpha of 0.05 and a power of 0.80 in a one-sided test,

resulting in 36 subjects required to recognize a statistically significant improvement in HAQ DI (-0.21). Then, given the importance of other secondary endpoints, an improvement of 9.9 ± 25 hours of work time lost requires 40 subjects. However, since it is expected that approximately half the study population may no longer be working due to their age, we assume a 50% employment rate in the study population and a drop-out rate of 10%, eventually approximately 89 patients will be required to achieve the required number of respondents.

Data Analysis:

Primary Endpoint Analysis

Change in HAQ DI score at 24 weeks after the initiation of adalimumab (observed population). This change will be summarized as the mean and 95% confidence interval and will be tested with a paired t-test.

Secondary Endpoint Analysis

- Change in other PROs (SF-36 domain scales, EQ-5D Index, WPAI total lost productivity) at weeks 12 and 24 after the initiation of adalimumab (observed population). These changes will be summarized as the means and 95% confidence intervals and will be tested with paired t-tests.
- Number and percent of patients achieving a clinically meaningful improvement on the HAQ DI, as defined by a -0.22 point improvement or greater, at weeks 12 and 24 after the initiation of adalimumab (observed population).

Additional Secondary Endpoint Analysis

- Change in HAQ DI score at 24 weeks after the initiation of adalimumab (observed population), compared with those patients not continuing on adalimumab (non-observeds). The mean changes in these two groups will be compared using an independent t-test.
- HCRU will be described using number and percentage within each category (number of consultations, number of procedures received, number of surgeries, number of hospitalizations and length of stay, number of concomitant medications)
- Associations between disease severity and PROs
- Associations between change in disease severity and change in PROs

Exploratory endpoint

- Change in patient satisfaction questions at weeks 12 and 24 after the initiation of adalimumab (observed population). These changes will be summarized as number and percentage of each response and compared with Kruskal-Wallis test. Satisfaction will also be dichotomized and analyzed over time with

Cochrane-Armitage test for trends.

Milestones:

Start of Data Collection : 19 Oct, 2015

End of Data Collection : 28 Feb, 2018

Study Progress Report : Not applicable

Interim Report : Not applicable

Registration in the EU PASS Register : Not Applicable

Final Report of Study Results : 31 Aug, 2018

5.0 Amendments and Updates

Number	Date	Section of Study Protocol	Amendment or Update	Reason
1	26 Dec 2017	- Sample size - Milestones	Amendment	Change of sample size and milestones (See Appendix L for details)

6.0 Milestones

Major study milestones and their planned dates are as follows:

Start of Data Collection (FPFV):	19 October 2015
End of Data Collection:	28 February 2018
Study Progress Report:	Not Applicable
Interim Report:	Not Applicable
Registration in the EU PAS register:	Not Applicable
Final Report of Study Results:	31 August 2018

7.0 Rationale and Background

Disability has been defined as impairments, activity limitations and participation restrictions due to personal and environmental factors (1). The concept of disability is one where a physical health condition or disease is evaluated in terms of its impact, difficulties, or limitations on a range of tasks, activities, or roles that are considered typical of everyday life. Examples of affected activities include basic aspects of daily living such as eating, bathing, dressing, household chores and meal preparation, or participation in society, or participation in work.

For public health purposes disability is becoming increasingly important as an outcome measure. Despite this, no data, within our knowledge, on the effectiveness of adalimumab on health-related QoL and work productivity in patients with Rheumatoid Arthritis (RA) in Korea.

Results from study of effect of adalimumab on Work Productivity and Activity Impairment (WPAI) scores and other Patient-Reported Outcomes (PROs) of work activity and well-being will be of interest to a variety of stakeholders in the healthcare system including patients, healthcare practitioners and payers in Korea.

Reimbursement in Korea is strongly influenced by local “real -world” evidence of the intervention’s effects on outcomes and economic endpoints. Therefore, having the economic and health outcomes “real world evidence” (RWE) for the use of Humira in moderate RA patients from Korea will be valuable to support the reimbursement / pricing maintenance and expansion in Korea.

In Korea, Humira is reimbursed for both moderate and severe RA patients. However, the recent policy change in Korea indicated that the paradigm of using the ICER as the only value metric has been recently shifting toward considering other criteria such as patient reported outcomes, equity, innovation, and affordability. For example, the Korean government is in discussion with industry and academics to incorporate multi-criteria decision analysis (MCDA) such as including patient reported outcome into HTA for new medical technologies and post launch product price management. In this regard, generating the RWE is critical for the price re-negotiation and protection with the national payer, under current reimbursement and pricing policies in South Korea.

The objective of this non-interventional, observational study is to assess the effect of adalimumab on health-related QoL, work productivity, and healthcare resource utilization (HCRU) in patients with RA in Korea.

The Humira’s efficacy and patient’s outcomes data from this study could be used to mitigate the tapering issues of biologics. The patients’ work-productivity data aligned with global comparison could be used to keep the current co-payment ratio, 10% of patients. And aligned with T2T and fit for work data, we can pursue to expand the importance of early treatment of RA.

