9.2 Setting

The study will take place in single country (Korea) with multiple centers. The study sites will be identified and selected by AbbVie. The study population shall comprise of male

and/or female patients who are attending a routine clinical visit and meet all of the inclusion criteria and none of the exclusion criteria. Overall, approximately 89 subjects with clinically diagnosed RA are planned to be enrolled in the study at up to 9 sites.

The recruiting investigators will select potentially eligible patients from consecutive visits within their clinic based on the inclusion and exclusion criteria (Section 9.2.1 and Section 9.2.2). It is the responsibility of each physician to ask every consecutive patient who meets the inclusion criteria of the study to participate to avoid selection bias, and if investigators hold different types of clinics (e.g. routine visit clinics versus emergency clinics), only patients visiting their routine clinics will be used for patient selection. Site personnel should thoroughly assess the eligibility criteria and evidence of this should be stored with the source documentation at site.

Where there is any deviation from the inclusion/exclusion criteria, the patient should be excluded from the study.

9.2.1 Inclusion Criteria:

Patients meeting all of the following inclusion criteria at baseline will be included:

1. Subject has a diagnosis of RA as defined by the 1987 revised ACR classification criteria and/or the ACR/ the European League against Rheumatism (EULAR) 2010 classification criteria (any duration since diagnosis)
2. Male or female subjects ≥ 18 years of age (local definition according to adalimumab label) who is in compliance with eligibility for adalimumab based on the local label
3. Patients with moderate to severe RA defined as DAS28 (ESR) or DAS28 (CRP) >3.2
4. Biologically treatment naïve and initiated adalimumab at baseline visit
5. Availability of clinical data of the previous 12 weeks prior to baseline
6. Ability to self-complete patient questionnaires
7. Subject must be able and willing to provide written informed consent and comply with the requirements of this study protocol

9.2.2 Exclusion Criteria:

Patients meeting any of the following exclusion criteria at baseline will be excluded:

1. Patients who are pregnant or breast feeding at enrolment or wish to become pregnant in the next 24 weeks

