9.7.2 Analyzable population

All subjects who received at least one dose of adalimumab during the study will be included. The main analysis will be conducted on the pooled population, where appropriate, with each individual country analyzed separately as supportive data.

9.7.3**Planned Methods of Statistical Analysis**

All statistical tests will be two-tailed with a significance level of 0.05. Descriptive statistics will be provided. Descriptive analysis will be conducted on all key parameters and presented as mean, standard deviation, minimum, maximum, and median when continuous and as “n” and percent when categorical. Change from adalimumab initiation to 24 weeks will be calculated and evaluated for significant improvements using paired t-tests / ANOVA for parametric and Wilcoxon signed-rank for non-parametric data. Analysis will be also be conducted by severity level (moderate vs severe), disease duration quartile (to compare to prior work) and up to two (2) other subgroups. Cochran-Armitage test of trends or other similar methods may be used to compare categories of subjects.

9.7.4**Primary Endpoint Analysis**

The primary endpoint variable will be the change in HAQ DI score at 24 weeks after the initiation of adalimumab (observed population).

The objective of the primary endpoint analysis will be to demonstrate that treatment with adalimumab improves functioning as measured by the HAQ DI in subjects with RA following treatment initiation. This change will be summarized as the mean and 95% confidence interval and will be tested with a paired t-test.

The primary analysis will be summarized as the mean and 95% confidence interval and will be tested with a paired t-test without adjusting for baseline disease severity. For sensitivity analysis, the mean change in HAQ DI at Week 24 will be analyzed using ANOVA adjusting for baseline disease severity.

9.7.5**Secondary Endpoint Analysis**

The main secondary endpoint variable will be the change in HAQ DI at 12 weeks after the initiation of adalimumab.

The objective of endpoint analysis will be to demonstrate that treatment with adalimumab improves functioning as measured by HAQ DI in subjects with RA compared to baseline.

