## 1. INTRODUCTION

### 1.1 Study Rationale and Background

Disability has been defined as impairments, activity limitations and participation restrictions due to personal and environmental factors (1). The concept of disability is one where a physical health condition or disease is evaluated in terms of its impact, difficulties, or limitations on a range of tasks, activities, or roles that are considered typical of everyday life. Examples of affected activities include basic aspects of daily living such as eating, bathing, dressing, household chores and meal preparation, or participation in society, or participation in work.

For public health purposes disability is becoming increasingly important as an outcome measure. Despite this, no data, within our knowledge, exist on the effectiveness of adalimumab on health-related QoL and work productivity in patients with Rheumatoid Arthritis (RA) in China, South Korea, and Taiwan.

Results from a study of the effect of adalimumab on Work Productivity and Activity Impairment (WPAI) scores and other Patient-Reported Outcomes (PROs) of work activity and well-being will be of interest to a variety of stakeholders in the healthcare system, including patients, healthcare practitioners and payers in China, South Korea and Taiwan.

Reimbursement in Taiwan and South Korea is strongly influenced by local “real - world” evidence of the intervention’s effects on outcomes and economic endpoints. The Chinese government has for some time been deeply concerned with an impending productivity decrease associated with ageing and chronic illnesses, including musculoskeletal disorders. These concerns have a large impact on their health financing and structuring policies. Therefore, having economic and health outcomes “real world evidence” (RWE) for the use of Humira (Adalimumab) in moderate RA patients from South Korea, Taiwan and China will be valuable to support the reimbursement / pricing maintenance and expansion in these countries.

In addition, the Bureau of National Health Insurance (BNHI) in Taiwan endorsed Dose Tapering and Withdraw (DT&W) guideline that was effective in Jan 2013. Under the DT&W policy, it indicated that when a patient with RA who is on Humira for more than 2 years, regardless of his/her disease state, will be tapered to 50% less dosage for 12 months and then to zero dosage after being tapered over one year. The government aims to implement DT&W policy to reduce the total health care spending

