## 5.3 Analysis Plan for Primary Objectives

The objective of the primary endpoint analysis will be to demonstrate that treatment with adalimumab improves functioning as measured by the HAQ DI score in subjects with RA following treatment initiation (i.e. baseline).

- The changes in HAQ DI score at 12 and 24 weeks after the initiation of adalimumab will be presented (Excel Table 3.1); these changes will be summarized as the mean, SD, minimum, maximum, median, 95% confidence interval; as well as the number and percent of patients achieving a clinically meaningful improvement on the HAQ DI, as defined by a -0.22 point improvement or greater. In addition, the mean change will be tested with a paired t-test without adjusting for baseline disease severity, shown by p-value1; for sensitivity analysis, the mean change will be analyzed using ANOVA adjusting for baseline disease severity, shown by p-value2 in the table.
- The change in HAQ DI score at 24 weeks after the initiation of adalimumab (mean, SD, minimum, maximum, median, 95% confidence interval), in those patients continuing on adalimumab (responder population) will be compared with those patients not continuing on adalimumab (non-responders). The mean

changes in these two groups will be compared using an independent t-test with p-value listed in the table (Excel Table 3.2).

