## 5.6 Analysis Plan for Exploratory Objective

- In Excel Table 10, separate multivariate generalized linear models (GLM) will be estimated to test for the differential changes in primary and secondary efficacy outcomes after baseline, across the subgroups defined by the potential modifiers, including age, gender, baseline severity, and other diagnoses/comorbidities.

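### The SAP text does not carry out the protocol's moderate-versus-severe analysis, so no mean change with confidence interval is specified for moderate RA

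*Protocol*

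**What the plan says.** Protocol 7.0 gives, as one use of the study, real-world evidence "for the use of Humira in moderate RA patients from Korea will be valuable to support the reimbursement" and pricing position. SAP 1.1 repeats this for three countries: evidence "in moderate RA patients from South Korea, Taiwan and China will be valuable to support the reimbursement".

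Enrolment is wider than that. Protocol 9.2.1 admits "Patients with moderate to severe RA defined as DAS28 (ESR) or DAS28 (CRP) >3.2", with no upper limit, so patients above 5.1 (severe in SAP 3.5.2) enter the same analysis set.

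On analysis, Protocol 9.7.3 is unconditional: "Analysis will be also be conducted by severity level (moderate vs severe"). Protocol 9.7.8 adds general linear models to test baseline severity, among other factors, as an effect modifier.

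The SAP handles severity as follows.

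- **Section 5.3, Table 3.1:** a pooled paired t-test of the HAQ DI change. For sensitivity, "the mean change will be analyzed using ANOVA adjusting for baseline disease severity", reported as a second p-value.
- **Section 5.4, Tables 4, 5 and 6:** changes in SF-36, EQ-5D-3L and WPAI with means, CIs and paired t-tests, and no breakdown by severity.
- **Section 5.5, Tables 9.1 and 9.2:** regressions relating each PRO to DAS28, and change in PRO to change in DAS28.
- **Section 5.6, Table 10:** models "to test for the differential changes in primary and secondary efficacy outcomes after baseline" across subgroups, baseline severity being one of them.

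Section 5.1 sets presentation by country as the default. No table title in the Section 6 list mentions results by severity level. The shells are in a separate workbook that is not among the documents.

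**The concern.** The protocol promises an analysis that the SAP text does not specify. Because Protocol 9.7.1 has all analysis follow the approved SAP, an analysis missing from the SAP may not be run.

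The pooled mean change is a weighted average of the moderate and severe means, and the weights are whatever mix happens to enrol. If patients with more severe disease improve more, a pooled mean can look good while moderate patients change little. Both documents give moderate RA as a group for which the evidence is wanted, so a reader of the report may apply the pooled figure to that group without any table showing whether it applies.

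The severity analyses that the SAP does contain answer other questions. A severity-adjusted p-value concerns the overall change. A DAS28 regression gives a slope. A test of differential change asks whether the groups differ. None is stated to report how much moderate patients changed and how precisely that is known.

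**Working it through.** **1. The plan's own figures.** Protocol 9.5 uses one-sided alpha 0.05 and power 0.80, with n = (SD x (1.645 + 0.842) / delta)^2.

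- HAQ DI: (0.5 x 2.487 / 0.21)^2 = 35.1, rounded up to 36.
- WPAI: (25 x 2.487 / 9.9)^2 = 39.4, rounded up to 40.
- Enrolment: 40 / 0.5 / 0.9 = 88.9, rounded up to 89.

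All three reproduce. Completers: 89 x 0.9 = 80.1, taken as 80. With a change of -0.21 and SD 0.5, a two-sided paired t-test in 80 patients has about 96% power.

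**2. Can severe patients alone carry the pooled result?** Assumptions not in the documents: moderate share p, zero change in moderate patients, SD 0.5 within each group. To keep the planned pooled mean of -0.21, the severe mean is d = -0.21 / (1 - p). The pooled SD is sqrt(0.25 + p(1 - p)d^2). Power is for the two-sided paired t-test at 0.05 (Protocol 9.7.3) with n = 80, from the noncentral t.

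| Moderate share | Severe mean change | Pooled SD | Chance of a significant pooled test |
|---|---|---|---|
| 30% | -0.30 | 0.519 | 94.7% |
| 50% | -0.42 | 0.542 | 92.8% |
| 70% | -0.70 | 0.594 | 87.8% |

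**3. Would a contrast of the Table 10 type show it?** Normal approximation for a simple two-group contrast: SE = 0.5 x sqrt(1/n_mod + 1/n_sev), power = Phi(difference / SE - 1.96).

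| Moderate share (n_mod / n_sev) | SE | Power for the step 2 difference | Power for a difference of 0.21 |
|---|---|---|---|
| 30% (24 / 56) | 0.122 | 69% (difference 0.30) | 41% |
| 50% (40 / 40) | 0.112 | 96% (difference 0.42) | 47% |
| 70% (56 / 24) | 0.122 | near 100% (difference 0.70) | 41% |

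The extreme split is usually detected when at least half the patients are moderate, and less reliably at a 30% share. Smaller differences would be missed more often than not. Table 10 is described as a multivariable model and the coding of severity is not stated, so these figures approximate its power.

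**4. What a moderate row would deliver.** The 95% CI half-width is t x 0.5 / sqrt(n). Power is two-sided for a change of -0.21.

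| Moderate patients | Half-width | Power |
|---|---|---|
| 24 | 0.21 | 51% |
| 40 | 0.16 | 74% |
| 56 | 0.13 | 87% |

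Against the 0.22 improvement threshold used in the SAP, such an interval is informative, though only just at n = 24. For work impairment in Table 6 the numbers are smaller: with half the patients moderate and half employed, 80 x 0.5 x 0.5 = 20.

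**5. Who counts as moderate.** SAP 3.5.2 has one formula with 0.70 x ln(ESR or CRP). Protocol 9.2.4.7 has a separate CRP version with 0.36 x ln(CRP) + 0.96. For the same joint counts and the same global assessment term, the SAP score minus the protocol CRP score is 0.34 x ln(CRP) - 0.96. At illustrative values, CRP 5 mg/L gives 0.34 x 1.609 - 0.96 = -0.41, and CRP 50 mg/L gives 0.34 x 3.912 - 0.96 = +0.37. Shifts of that size can move a patient across the 5.1 or 3.2 boundary.

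**The case against.** The strongest reply is that pooling is right for this study. Reimbursement context in the same section covers both groups: "In Korea, Humira is reimbursed for both moderate and severe RA patients". The stated objective is effects on quality of life, work productivity and "healthcare resource utilization (HCRU) in patients with RA in Korea", with no severity limit, and eligibility is moderate to severe. A pooled primary result matches that objective and population. This stands: a reader might infer that moderate RA is the purpose of the study and that the pooled primary is misdirected, but the documents support only that moderate RA is one named use.

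A reader might also infer that every SAP table ignores severity and that the results will say nothing about moderate patients. That goes too far. Table 10 tests differential change by baseline severity, Table 3.1 has a severity-adjusted p-value, Tables 9.1 and 9.2 use DAS28, and Table 2 reports the baseline DAS28 mix. In the 50/50 illustration a simple contrast would have about 96% power.

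The reply also notes that Protocol 9.7.1 describes the SAP as including the protocol's analyses and adding to them, so the by-severity analysis has not been withdrawn, and that the shells may contain it. Both points are fair. They are reasons to state the analysis in the SAP, because nobody can tell from the SAP text that it will be produced. The disease-duration quartile analysis promised in the same protocol sentence is also missing from the SAP tables, which suggests the sentence was not carried over.

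Finally, the moderate share and the zero-change scenario are assumptions. That is correct: the calculation shows what a pooled result could conceal and gives no indication that this is likely.

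**Conclusion.** The point holds as a gap between protocol and SAP. Protocol 9.7.3 commits to a moderate-versus-severe analysis, both documents name moderate RA as a use of the evidence, and the SAP text specifies no mean change with CI in moderate patients. A significant pooled test is compatible with no change in that group: about 93% of studies would be significant at a 50% moderate share, and 88-95% across shares of 70-30%. The contrast in Table 10 would usually show the extreme case at a 50% share or above, but has about 41-47% power for a difference of 0.21, and a non-significant result there would not show that moderate patients improved.

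These figures rest on 80 completers and a within-group SD of 0.5 (derived from Protocol 9.5), and on assumed severity shares and group means. The pooled primary analysis is not in error, and the finding concerns the SAP text only, since the shells were not seen. It should be corrected because the protocol already requires the analysis and the cost is small.

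**What to change.** 1. Reconcile the DAS28 formula in SAP 3.5.2 with the two formulas in Protocol 9.2.4.7, and state which score classifies a patient who has both ESR and CRP. This comes first because it fixes the severity groups.
2. In SAP 5.3 and 5.4, add rows to Tables 3.1, 4, 5 and 6 by baseline DAS28 category (moderate: above 3.2 up to 5.1; severe: above 5.1), giving n, mean change and 95% CI at Weeks 12 and 24.
3. Keep the pooled Week 24 HAQ DI change as primary. Label the rows supportive estimates of limited precision, with a half-width of about 0.21 to 0.13 for 24 to 56 moderate patients.
4. State that the report will make no moderate-specific claim from the pooled result alone.
5. If the shells already contain such rows, say so in the SAP text.

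The cost is SAP wording and extra table rows from data already collected. The drawback is wide intervals in the severity rows, above all for work impairment, where only employed patients contribute.
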